5.6. LV VECTORS AND PACING CONFIGURATIONS

The 14 LV vectors considered in this study are:

Table 2: LV tests

#	IS1 lead	IS4 lead
1	LVtip-LVring	LVtip1-LV2
2	LVtip-RVring	LVtip1-RVring
3	LVtip-RVcoil	LVtip1-RVcoil
4	LVtip-CAN	LVtip1-CAN
5	LVring-RVcoil	LV2-RVcoil
6	LVring-CAN	LV2-CAN
7		LVtip1-LV4
8		LV2-LV4
9		LV3-LV2
10		LV3-LV4
11		LV3-RVring
12		LV3-RVcoil
13		LV3-CAN
14		LV4-RVcoil

LEVEA – Statistical Analysis Plan

Three LV pacing configurations are considered in this study to perform “In-Clinic LVAT” tests for all eligible LV pacing vectors:

- DDD A-test (atrium overdrive)
- DDD P-test (no atrium overdrive)
- VVI test

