10.4. EVALUATION OF THE APPLICABILITY OF THE ALGORITHM

The algorithm may not be applicable to some subjects, mainly because of a very long inter-ventricular conduction delay (VV delay). A subject is defined as “eligible” if he/she has at least one complete LV vector test in either of the M0 or M1 visit.

The endpoints for the applicability of the algorithm in the population are:

- A. The number and percentage of subjects who are “eligible” to receive the algorithm. Percentage will be calculated based on the total number of subjects included in the EP, that is:

Number of subjects with at least one complete LV Vector Test at M0 or M1 visits/ Total Number of subjects in EP.

- B. For subject having IS1 lead, up to 6 LV vector tests over 3 LV pacing configurations will be attempted for each subject at each visit.

Among all the subjects having IS1 leads, the number and percentage of subjects having no, one, two,..., six Attempted, Completed and Successful LV vector tests will be presented by LV pacing configuration and visit.

Among all the subjects having IS4 leads, the number and percentage of subjects having one, two,..., fourteen Attempted, Completed and Successful LV vector tests will be presented by LV pacing configuration and visit.

Only subjects with non-missing manual data will be considered.

Percentages calculated based on the number of subjects in EP with the respective lead and configuration will be presented for Attempted, Completed and Successful LV tests.

This information will also be presented with the help of histograms.

This analysis will be based on EP.

This will also be listed.

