13. ADDITIONAL EXPLORATORY ANALYSIS

Whenever a Statistical test is performed for an Additional Analysis, it is of hypothesis generating and descriptive in nature.

13.1. ACCURATE DETERMINATION OF HIGH PACING THRESHOLD VALUE (NO CAPTURE OR >5V) : ALGORITHM Vs. INDEPENDENT REVIEWER

All LV vector tests are done at a starting amplitude of 5V for all LV pacing configurations. Therefore, if the LV threshold value is > 5 V or if there is no capture at the starting amplitude for the tested LV vector, then the algorithm identifies the LV threshold value as a high pacing threshold “> 5V”.

Number and percentage of correct determination of high pacing threshold value (>5V) provided by the algorithm feature and an independent reviewer, on all LV pacing vectors and all LV pacing configurations available at M0 visit will be presented. Percentage will be based on all subjects included in the M0-ITT.

A Fisher exact test will be performed to test the significance of association between accurate determination provided by the algorithm feature and the independent reviewer. The two-sided p-value will be presented.

In addition, the Sensitivity and Specificity as defined below will also be presented:

i. Sensitivity or Probability (Algorithm feature = High Pacing Threshold | Independent reviewer = High Pacing Threshold) = $TP/(TP+FN)$

i. Specificity or Probability (Algorithm feature = Not High Pacing Threshold | Independent reviewer = Not High Pacing Threshold) = $TN/(FP + TN)$

13.2. ASSESSMENT OF CONSISTENCY OF “IN-CLINIC LVAT” TEST BETWEEN M0 AND M1 VISITS: COMPARISON TO MANUAL LV THRESHOLD TESTS RESULTS

At each of the two subject visits, success rate will be calculated for each LV vector and each LV pacing configuration based on M0-ITT and M1-ITT respectively. As we have up to 14 LV vectors and 3 configurations, we will have a total of 42 success rates at each M0 and M1 visits.

Null Hypothesis: The Success-rate for LV tests at M0 visit = The success rate for LV tests at M1 visit

LEVEA – Statistical Analysis Plan

Alternative Hypothesis: The Success-rate for LV tests at M0 visit \neq The success-rate for LV tests at M1 visit.

A paired t-test will be performed to test if the mean difference of the success rate over the two visits is significantly different from 0. A two-sided p-value will be presented. This will be performed by configuration and overall. The mean difference and its 95% CI will also be presented.

This analysis will be performed on ITT.

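### SAP 13.1: the only inference on algorithm-reviewer agreement for high thresholds is an unclustered Fisher test of association, while sensitivity and specificity carry no interval

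*SAP*

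**What the plan says.** SAP 13.1 asks whether the algorithm and the independent reviewer agree that a vector has a high threshold (above 5 V, or no capture at the 5 V starting amplitude). It plans the following:

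- **Counts and percentages.** Correct determinations "on all LV pacing vectors and all LV pacing configurations available at M0 visit will be presented". The denominator, however, is subjects: "Percentage will be based on all subjects included in the M0-ITT".
- **A test.** "A Fisher exact test will be performed to test the significance of association between accurate determination", between algorithm and reviewer. "The two-sided p-value will be presented". No significance level or decision rule is attached.
- **Agreement measures.** "In addition, the Sensitivity and Specificity as defined below will also be presented", each with its formula in true and false positives and negatives. No confidence interval is named.

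Section 13 opens by saying of any test in it that "it is of hypothesis generating and descriptive in nature".

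Two other places fix how many results one subject can contribute. SAP 10.4 says that for an IS1 lead "up to 6 LV vector tests over 3 LV pacing configurations will be attempted for each subject at each visit". For IS4, SAP 5.6 gives the list: "The 14 LV vectors considered in this study are" set out in its Table 2, with three pacing configurations.

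**The concern.** Three features of 13.1 do not fit its purpose.

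1. **The null hypothesis.** Fisher's test asks whether the algorithm's call is unrelated to the reviewer's. Under SAP 10.1 the reviewer adjudicates electrogram strips recorded during the same automatic test, so complete independence is hardly a plausible null. Rejecting it shows only that the algorithm does better than chance, not how often it is right.
2. **The unit.** The table pools every vector and configuration, so one subject supplies many entries. Nothing in 13.1 allows for correlation within a subject.
3. **The missing intervals.** The exact-interval statement that opens SAP Section 10 covers secondary and ancillary endpoints, not Section 13. The general rule in SAP 17.2 lists a confidence interval for continuous variables only. Sensitivity and specificity therefore have no stated precision, although 10.1, 12.1, 12.2 and 13.2 all plan intervals.

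What is at stake is interpretation. A very small p-value may be taken as showing that the algorithm reliably flags vectors that do not capture, when it shows much less.

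**Working it through.** **Inputs from the documents.** Evaluable subjects: 47, from SAP 2.3 (231/5 = 46.2, rounded up). Tests per subject at M0: up to 6 × 3 = 18 for IS1 (SAP 10.4) and up to 14 × 3 = 42 for IS4 (SAP 5.6). The documents give no sample size, power or expected result for 13.1, so there is no planned figure to reproduce there. The 231 behind the 47 does reproduce: it is the smallest n at which the exact one-sided binomial test of 90% against 95% reaches 80% power (217 or more successes, alpha 0.0239, power 0.816).

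**Inputs assumed.** Test count: 47 × 5 = 235 as a low case, and 47 × 5 × 3 = 705. Share of tests above 5 V according to the reviewer: 2%, 5%, 10%. Algorithm specificity 90%, sensitivity 30% or 50%. Intraclass correlation (ICC): 0.1, 0.3, 0.5.

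**Step 1: Fisher p-value for a poor algorithm.** For N tests and prevalence π, the expected table is TP = Nπ × sensitivity, FN = Nπ − TP, TN = N(1 − π) × specificity, FP = N(1 − π) − TN, each rounded to whole tests. The two-sided exact test gives:

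| Tests | Above 5 V | p, sensitivity 30% | p, sensitivity 50% |
|---|---|---|---|
| 235 | 2% | 0.089 | 0.089 |
| 235 | 5% | 0.032 | 9.5e-4 |
| 235 | 10% | 0.013 | 7.1e-6 |
| 705 | 2% | 0.047 | 2.4e-4 |
| 705 | 5% | 0.0026 | 4.5e-9 |
| 705 | 10% | 1.3e-5 | 8.3e-15 |

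At 235 tests and 2% there are only 5 positives. Both sensitivities then round to 2 detected, which is why the first row repeats.

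**Step 2: what that p-value hides.** Take the last cell: TP 35, FP 63, FN 35, TN 572.

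- Sensitivity = 35/70 = 50%; half of the high thresholds are missed.
- Positive predictive value = 35/98 = 36%.
- Observed agreement = (35 + 572)/705 = 0.861.
- Chance agreement = (98 × 70 + 607 × 635)/705² = 0.789.
- Kappa = (0.861 − 0.789)/(1 − 0.789) = 0.34.

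The p-value is 8e-15. The estimates show the weakness and the test does not.

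**Step 3: does the test hold its level?** In simulation, algorithm and reviewer calls each followed a beta-binomial distribution by subject (47 subjects, prevalence 10% or 20%, 2,000 runs) and were unrelated to each other. A nominal 5% Fisher test rejected as follows:

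| Tests per subject | ICC 0.1 | ICC 0.3 | ICC 0.5 |
|---|---|---|---|
| 5 | 4% | 6–8% | 9–15% |
| 15 | 6% | 16–17% | 31–36% |
| 18 | 5–6% | 16–19% | 35–39% |

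With 15 to 18 tests per subject the level is close to nominal at ICC 0.1 and clearly inflated from about 0.3.

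**The case against.** The strongest reply is that the plan does not rest accuracy on this p-value. Percent correct comes first in 13.1, sensitivity and specificity sit in the same subsection, and a sensitivity of 30% would be printed next to the test. Section 13 declares its tests descriptive, and no success criterion uses the result. The main comparison with the reviewer is SAP 10.1, a secondary endpoint covering all vectors and configurations at M0. It counts a result above 5 V from both sources as accurate and gives an exact 95% interval. All of this stands, and it keeps the matter small. It does not close the gap: the 10.1 interval covers overall accuracy rather than the high-threshold question, and it too ignores clustering.

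A reader might go further and infer that almost any algorithm would give a highly significant result. The documents do not support that, because they state neither the number of tests nor how often thresholds exceed 5 V. In 1,000 simulated trials with independent tests, sensitivity 30%, specificity 90% and prevalence 5%, p fell below 0.05 in 43% with 235 tests and in 87% with 705. Significance for a poor algorithm is likely at the larger counts but not assured.

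Nor can serious inflation from clustering be taken as established. No ICC is given, and at 0.1 the effect is slight. The figure of 42 tests is the maximum for an IS4 subject, not typical of everyone.

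**Conclusion.** The point holds as a cheap improvement. As written, the only inference in SAP 13.1 is a test against chance. It does not measure agreement, makes no allowance for repeated tests in a subject, and stands beside sensitivity and specificity with no interval. Under the assumptions shown, an algorithm that detects 30% to 50% of high thresholds gives p from 0.09 down to 8e-15, depending mainly on test count and prevalence. A small p-value is therefore no evidence of accuracy. With 15 to 18 tests per subject, the type I error of a nominal 5% test is about 6% at ICC 0.1 and 16–19% at ICC 0.3. Test count, prevalence, sensitivity, specificity and ICC are all assumed.

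It would be wrong to conclude that the SAP judges agreement by Fisher's test alone, or that the primary or secondary conclusions are affected. Neither follows from the text.

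**What to change.** In SAP 13.1:

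1. Remove the Fisher exact test.
2. Report sensitivity and specificity, and optionally kappa, each with a 95% confidence interval from a bootstrap that resamples subjects or from another cluster-robust method.
3. State that counts and percentages use LV vector tests as the denominator, and give the number of contributing subjects alongside. If few subjects supply the results above 5 V, that number tells the reader how far to trust the interval.

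The cost is a few lines of code and the loss of one descriptive p-value. No new data are needed, and no other analysis changes.

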4.1.2. Primary endpoint

The primary endpoint of the study is the success rate of “In-Clinic LVAT” test.

The success is defined by a LV threshold value identified automatically by “In-Clinic LVAT” feature equivalent to the manual threshold test value performed by physician on at least 90% among complete tests (performance goal).

For the primary endpoint, the evaluation is performed on 5 LV pacing vectors common to IS1 and IS4 leads: LV bipolar, LVring-RVcoil, LVtip-can, LVtip-RVcoil, and LVring-can pacing vectors. Test will be evaluated at different pacing conditions: DDD A-test and VVI. Results will be analyzed irrespective of the type of lead used (bipolar or quadripolar) and in any test configuration (DDD A-test or VVI).

An equivalent LV threshold value is defined as the same value of automatic and manual LV threshold tests, with a flexibility of ± 2 steps (meaning $\pm 0.5V$ if threshold $< 2.5V$, else $\pm 1V$ as measured in 2 consecutive cardiac cycles). A margin of ± 2 steps is accepted because of the variability of the threshold, and due to the design of the algorithm.

Among all the eligible complete LV Vector Tests collected, only those performed in DDD A-test with atrial overdrive pacing configuration (if available, otherwise in VVI) and with a manual LV threshold test performed in the same conditions and reported in the electronic Case Report Form (eCRF) will be retained. Only one LV Vector Test per LV pacing vector per subject will be analyzed.

In case several LV Vector Tests were eligible with the same LV pacing vector, for the same subject, on 2 different follow-ups, only M0 data will be considered.

The primary analysis is based on at least 231 complete LV Vector Tests provided by the algorithm and collected at M0. If data at M0 is unavailable, then corresponding data collected at M1 will be considered.

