6.1. TREATMENT AND EVALUATION

6.1.1. *Inclusion follow-up*

Subjects must be informed about the investigation and the potential benefits and risks of the study prior to enrollment. Only those subjects who voluntarily provide written consent to participate will be eligible for enrollment.

The following procedures must be conducted before inclusion of the subject in the study:

- Evaluate subject eligibility based on the inclusion and exclusion criteria
- Obtain written informed consent
- Source data that demonstrate conformance with inclusion criteria should be retained at the investigational site

The following procedures must be conducted in order to include the subject in the study:

- Report implant information
- Report subject's medical history
- Report subject's clinical examination including current vital signs and NYHA classification
- Report subject's current concomitant medications (based on the EDC questions)

6.1.2. *M0 follow-up*

- Perform a complete interrogation of the device with the appropriate clinical programmer
- Print report file
- Measure P-R, A-R and V-V inter ventricular conduction durations on the EGM
- Launch manual LV threshold tests on:
 - 5 common LV vectors to IS1 and IS4 for all subjects,
 - 4 dedicated IS4 LV vectors for subject implanted with IS4 LV lead (LV2-LV4, LV3-LV4, LV3-LV2, LVtip1-LV4).

Manual tests should be performed prior to automatic test to limit bias.

Optional manual threshold tests on additional LV pacing vectors could be performed under physician discretion.

- ECG record:
 - Spontaneous rhythm,
 - Paced rhythm during “In-Clinic LVAT” test in DDD A-test for 30 seconds recording corresponding to 10 seconds before launching test and 20 seconds during the test.
- Launch “In-Clinic LVAT” test on all LV pacing vectors in following pacing configuration:
 - DDD A-test
 - DDD P-test
 - VVI
- Perform right ventricular pacing recordings data collection using RF telemetry to allow collection of multiple EGM:
 - RV A-test

- RV P-test
- Retrieve subject technical data analysis files
- Report Adverse Events and Serious Adverse Events occurred during the testing procedure if any
- Report Device Deficiencies if any

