6.1.3. M1 follow-up

- Perform a complete interrogation of the device with the appropriate clinical programmer
- Print report file
- Measure P-R, A-R and V-V inter ventricular conduction durations on the EGM
- Launch manual LV threshold tests on:
 - 5 common LV vectors to IS1 and IS4 for all subjects,
 - 4 dedicated IS4 LV pacing vectors for subject implanted with IS4 LV lead (LV3-can, LV3-RVring, LV3-RVcoil, LV4-RVcoil).

Manual tests should be performed prior to automatic test to limit bias.

Optional manual threshold tests on additional LV pacing vectors could be performed under physician discretion.

- ECG record:
 - Spontaneous rhythm,
 - Paced rhythm during “In-Clinic LVAT” in DDD A-test for 30 seconds recording corresponding to 10 seconds before launching test and 20 seconds during the test.
- Launch “In-Clinic LVAT” test on all LV pacing vectors in following pacing configuration:
 - DDD A-test
 - DDD P-test
 - VVI
- Perform right ventricular pacing recordings data collection using RF telemetry to allow collection of multiple EGM:
 - RV A-test
 - RV P-test
- Retrieve subject technical data analysis files
- Report Adverse Events and Serious Adverse Events occurred during the testing procedure if any
- Report Device Deficiencies if any
- Report Serious Cardiovascular Adverse Event occurred since last follow-up if any

6.1.4. *Unscheduled follow-ups*

If the subject comes in due to a serious cardiovascular adverse event, re-intervention, or if the subject’s device is interrogated for any reason outside of regular follow-up, the routine follow-up procedure should be performed when possible.

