For number of LV vector tests “completed”, the percentage will be calculated based on the number of LV vector tests attempted and for number of LV vector tests “accurate”, the percentage calculated based on number of Complete LV vector tests .

A heat plot will be presented for Attempted, Completed and Accurate percentages. If the percentage is > 90%, it will be coloured green, if the percentage is between 75% and 90% (inclusive), it will be coloured brown and if the percentage <75%, then it will be coloured orange.

This will also be listed.

For this analysis, EP will be used considering M0 visit only.

10.2. ASSESSMENT OF THE SUCCESS RATE OF “IN-CLINIC LVAT” TEST AT M0 VISIT: COMPARISON TO MANUAL LV THRESHOLD TESTS RESULTS

This endpoint is the success rate of “In-Clinic LVAT” feature on LV pacing vectors and LV pacing configurations available at M0 visit.

The threshold obtained from the “In-Clinic LVAT” feature, extracted from RTD files, will be compared against manual LV threshold values recorded in the eCRF. The definition of equivalence is same as that of primary analysis.

Test will be evaluated at different LV pacing configuration: DDD A-test, DDD P-test and VVI test. Among all the eligible complete LV Vector Tests collected, only those with a manual LV threshold test performed in the same conditions (same pacing pulse width) at M0 visit and reported in the electronic Case Report Form (eCRF) will be retained.

All analyses performed for this Secondary endpoint will be performed based on manual LV threshold tests results considering data only from M0 visit (except for testing of hypothesis and missing data imputation).

This Secondary endpoint will be based on M0-ITT population.

Decomposition of “In-Clinic LVAT” Success Rate by LV Vector and by LV pacing configuration at M0 visit

Only subjects with non-missing manual data will be considered.

Total number of attempted, completed and successful LV vector tests will be presented by LV vector for each LV pacing configuration.

For number of LV vector tests “attempted”, the percentage will be calculated based on the EP population.

For number of LV tests “completed”, the percentage will be calculated based on the number of LV vector tests attempted.

For number of LV vector tests “Successful”, the percentage will be calculated based on number of Complete LV vector tests.

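### SAP 13.2 (exploratory): 42 success rates per visit is a maximum; scheduled manual tests support 15 M0–M1 pairs, and the cell-level paired t-test can understate the standard error

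*SAP*

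**What the plan says.** SAP 13.2 asks whether agreement between algorithm and manual thresholds changes from M0 to M1. From up to 14 vectors and three pacing configurations it expects that "we will have a total of 42 success rates at each M0 and M1 visits". It specifies that "success rate will be calculated for each LV vector and each LV pacing configuration based on M0-ITT and M1-ITT respectively", and closes by naming ITT as the analysis population. A paired t-test on these rates, overall and by configuration, yields a two-sided p-value and a 95% CI for the mean difference. The opening of section 13 gives every test there exploratory status.

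Other sections determine which rates can exist:

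- SAP 5.6, Table 2, is introduced by "The 14 LV vectors considered in this study are". It has six vectors available on both lead types and eight on IS4 leads only.
- Protocol 6.1.2 and 6.1.3 schedule manual tests on five common vectors at both visits. Protocol 4.1.2 names these five: "LV bipolar, LVring-RVcoil, LVtip-can, LVtip-RVcoil, and LVring-can pacing vectors".
- For IS4 leads, M0 adds "4 dedicated IS4 LV vectors for subject implanted with IS4 LV lead (LV2-LV4, LV3-LV4, LV3-LV2, LVtip1-LV4"; M1 adds "4 dedicated IS4 LV pacing vectors for subject implanted with IS4 LV lead (LV3-can, LV3-RVring, LV3-RVcoil, LV4-RVcoil".
- Both visits carry the provision "Optional manual threshold tests on additional LV pacing vectors could be performed under physician discretion".
- SAP 10.2 retains "only those with a manual LV threshold test performed in the same conditions (same pacing pulse width) at M0 visit", and SAP 10.3 does the same for M1. SAP 5.7 defines a successful test by comparison with the manual value for the same subject, vector, pulse width and visit.

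**The concern.** There are two separate issues.

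**The count.** Without a manual value there is no success or failure, so a vector contributes a rate only where manual tests were made. The IS4 vectors scheduled at M0 and at M1 do not overlap, and LVtip-RVring (Table 2, row 2) is scheduled at neither visit. SAP 13.2 does not say that most of the 42 cells have no scheduled partner at the other visit, nor which pairs enter the test.

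**The unit of analysis.** The t-test takes each vector-by-configuration cell as an independent, equally weighted observation, yet the same subjects feed every cell. The manual tests are also listed by vector and not by configuration. Because the SAP glosses same conditions as same pulse width, one manual value can serve all three configurations, and an error in it moves three cells together. The rates come from M0-ITT and M1-ITT, which are both subsets of ITT but need not contain the same people.

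If the standard error is too small, a chance difference between visits could be reported as a change in algorithm performance, with an interval that is too narrow even when read descriptively.

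**Working it through.** **1. The stated figure.** 14 vectors × 3 configurations = 42. It reproduces.

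**2. What the schedule supports.**

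- M0: 5 common + 4 IS4-only (LV2-LV4, LV3-LV4, LV3-LV2, LVtip1-LV4) = 9 vectors; 9 × 3 = 27 rates.
- M1: 5 common + 4 IS4-only (LV3-can, LV3-RVring, LV3-RVcoil, LV4-RVcoil) = 9 vectors; 9 × 3 = 27 rates.
- Scheduled at both visits: the 5 common vectors; 5 × 3 = 15 pairs, or 5 per configuration.
- Scheduled at either visit: 5 + 4 + 4 = 13 of 14; LVtip-RVring is the one left out.

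**3. Why cell correlation matters.** For K cell differences with common correlation ρ, the true SE divided by the paired-t SE is √[(1 + (K−1)ρ)/(1−ρ)]. With K = 15:

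- ρ = 0 gives 1.00.
- ρ = 0.05 gives √(1.70/0.95) = 1.34.
- ρ = 0.10 gives √(2.40/0.90) = 1.63.

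Here ρ is the correlation of the *differences*. A stable subject effect therefore drops out when the same subjects are seen twice.

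**4. Size under the null.** Taken from the documents: 47 evaluable subjects and 95% success (SAP 2.3), 5 vectors, 3 configurations, 2 visits. Assumed, because the documents give neither: two-sided 5% for this test, and the correlations. Each result comes from a latent normal variable whose variance is split into shares for subject, subject-by-visit, a manual value shared by the three configurations, and residual. There were 3,000 to 6,000 runs per scenario. At 4,000 runs the Monte Carlo standard error near 5% is √(0.05 × 0.95/4000) = 0.3 points. Ranges cover repeated runs.

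| Assumed shares (subject, subject-by-visit, shared manual) | Overall, 15 cells | Per configuration, 5 cells |
|---|---|---|
| (0, 0, 0) | about 5% | about 5% |
| (0.3 to 0.5, 0, 0) | 4.6% to 5.5% | 4.6% to 4.9% |
| (0, 0, 0.3) | 6.4% to 7.2% | 4.7% |
| (0, 0, 0.6) | 11% to 12% | 4.7% |
| (0, 0.1 to 0.2, 0) | about 9% to 15% | not run |
| (0.2, 0.1, 0) | 12% | 6.2% |
| (0.2, 0.2, 0) | 19% to 20% | 8.5% |
| (0.2, 0.1, 0.4) | 18% to 19% | 6.3% to 6.5% |
| (0.2, 0.3, 0.3) | 33% to 35% | 11% |

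With 59 subjects at M0 and 47 of them at M1, the overall test rejects in about 5% with no correlation, 7.0% with a stable subject share of 0.3, and 9% to 10% with 0.5.

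A paired t-test on one mean M1−M0 difference per subject rejected in about 4% to 5% in every scenario.

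**The case against.** Section 13 is exploratory. SAP 13.2 sets no alpha and no decision rule, and no study conclusion depends on it. The 42 follows from an explicit *up to 14*, and is correct as a maximum. The algorithm is run on all vectors at both visits, and optional manual tests are allowed, so one tested subject is enough to create a rate. The number of optional tests made cannot be seen in the documents. The data extract named in SAP 17.8 carries the date 20180112 and SAP version 1.0 is dated 19 February 2018, so writing 27 and 15 as achieved counts could misdescribe the data. All of this stands: 15 is what the schedule provides and not a ceiling, and the weight of the point is low.

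It is also true that the inflation depends on correlations the documents do not give. Four stronger readings are tempting, and none is supported:

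- *The 42 invalidates the p-value.* It does not; a paired t-test takes its degrees of freedom from the pairs actually present.
- *Any clustering by subject inflates the error.* A stable subject effect in the same subjects cancels in the difference, and the test holds its level.
- *Different subjects at the two visits are enough.* With 59 and 47 subjects and no correlation the rate is about 5%; a stable subject effect is needed as well.
- *The 59/47 case is what the plan expects.* The plan applies 20% as overall attrition to reach 47 evaluable subjects. Placing all of it between the visits is an extreme assumption.

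What remains is that 13.2 states formal hypotheses and promises a p-value and a 95% CI. Exploratory status does not make a standard error that ignores shared subjects and shared manual values right.

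**Conclusion.** The point holds, at low severity. Scheduled manual tests support 27 rates per visit and 15 pairs (5 per configuration) against a stated 42 that is only the maximum. SAP 13.2 does not say which pairs enter the test.

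The overall standard error is too small under any of three conditions: a subject-by-visit effect; a manual value shared across configurations; or a stable subject effect combined with different subjects at the two visits. Under the assumed shares, rejection at nominal 5% is:

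- about 6% to 12% with the shared manual value only;
- about 9% to 15% with a subject-by-visit effect only;
- 12% to 20% when a stable subject share of 0.2 is added to the subject-by-visit effect;
- 18% to 35% with all three components;
- 7% to 10% in the 59/47 case with a stable effect.

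Per configuration the problem is smaller: about 5% with the shared manual value only, and 6% to 11% in the scenarios with a subject-by-visit effect, all of which also carried a stable share of 0.2.

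These are sizes under assumptions and not estimates for this trial. The primary endpoint and the sample size of 231 tests and 59 subjects are not affected.

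**What to change.** Change SAP 13.2 as follows:

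1. Say that 42 is the maximum, that the schedule supports 27 rates per visit and 15 pairs (5 per configuration), and that further pairs depend on optional manual tests. Report the number of pairs used.
2. Take the p-value and 95% CI from one mean M1−M0 difference per subject, analysed with a paired t-test, overall and by configuration. Build each difference from the subject-vector-configuration results that have a manual value at both visits, on the 5 vectors scheduled at both.
3. Report the cell-level rates and the other 9 vectors, including any optional pairs, descriptively with counts.

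A clustered model such as GEE would be another valid route. The subject-level t-test is the simplest and held its level in the runs above; a subject-level percentile bootstrap rejected in 4.9% to 8.2%.

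The cost is SAP wording and derivation code, with no new data. The downsides are real. Subjects without paired results and the other 9 vectors leave the test. The interval can widen with visit-level correlation, with a shared manual value, or with incomplete tests. In simulation with complete data, the mean 95% half-width (subject-level against 15-cell) was 2.0 to 2.3 against 2.2 to 2.4 percentage points without visit-level correlation or a shared manual value, and 2.5 to 4.3 against 2.1 to 2.4 with such correlation. With an assumed 30% of results missing and a stable subject share of 0.3, it was 3.25 against 2.83 points.
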